9.3.3 Removal of Subjects from Therapy or Assessment

The investigator may discontinue study drug or withdraw the subject from the study at any time for safety or administrative reasons. The subject may decide to stop study drug or withdraw from the study at any time for any reason.

Subjects who discontinue taking study drug prematurely for any reason will undergo an ED Visit within 7 days of their last dose of study drug (see [Section 9.1.2.2](#)). Follow-Up Visits will also be scheduled 4 and 12 weeks after the last dose of study drug (see [Section 9.1.2.3](#)). Subjects who discontinue study drug prematurely will also be scheduled to return to the study site for each scheduled visit when clinical efficacy assessments are to be conducted (ie, at Visits 11, 14, 15, 16, 17, and 18, if these visits have not already been performed). At these visits, only clinical efficacy assessments (MMSE, CDR, ADAS-cog₁₄, FAQ, CBB and ISLT) will be conducted. Regularly scheduled clinical efficacy visits do not need to be attended if they fall within 8 days (visit window) after the Early Discontinuation Visit or within ± 8 days of either of the Follow-Up Visits (Visit 19 and Visit 20). Subjects who discontinue early from study drug are considered on study as long as they return for their regularly scheduled clinical efficacy visits as outlined above.

The primary reason for discontinuation and all other reason(s) contributing to the subject's discontinuation from study drug(s) should be collected on the Subject Disposition eCRF page. In addition, the date of last dose of study drug(s) will be recorded on the Study Drug Dosing eCRF page. If a subject discontinues study drug and withdraws from the study at the same time, the ED Visit will be followed (see [Section 9.5.5](#)).

Safety-related criteria for discontinuation of study drug include the following:

- a. A study drug discontinuation threshold will be set based on absolute counts of CD4 (T helper cells), CD8 (cytotoxic T cells), or CD19 (B cells). The discontinuation threshold will be set at below the level of the LLN, at a level that represents a greater risk of opportunistic infection in the treated population. For CD4 (T helper cells) the discontinuation threshold is 250 cells/ μ L. For CD8 (cytotoxic T cells) and CD19 (B cells) the discontinuation thresholds are 150 cells/ μ L and 50 cells/ μ L, respectively. Any subject who has CD4 (T helper cells), CD8 (cytotoxic T cells), or CD19 (B cells) absolute counts below the discontinuation threshold as confirmed by a repeat test conducted within 1 week of the initial test will be discontinued from study drug.
- b. Subjects with CD4 (T helper cells), CD8 (cytotoxic T cells), or CD19 (B cells) absolute counts between the LLN and the discontinuation threshold will have lymphocyte subset counts performed on a weekly basis. Subjects with a >33% reduction from baseline in CD4 (T helper cells), CD8 (cytotoxic T cells), or CD19 (B cells) absolute counts will also have lymphocyte subset counts performed on a weekly basis. For these subjects, the decision as to whether the subject remains on study drug or is to be discontinued from study drug will be based upon clinical judgment and will take into account any clinical presentation in addition to the lymphocyte subset counts. These subjects may continue with treatment if there is no clinical evidence of infection. They will be discontinued from study drug if they have infections of a moderate to severe intensity (eg, subjects whose infections are not localized, or are systemically unwell, or who require systemic anti-infective drug treatment).

Table 1 Study Drug Actions for Lymphocyte Subset Absolute Counts

| Lymphocyte subset absolute counts | Action | Decision to continue or discontinue |
|--|---|---|
| CD4 (T helper cells), CD8 (cytotoxic T cells), or CD19 (B cells) absolute counts below discontinuation threshold | Retest within 1 week | If retest performed within 1 week confirms lymphocyte subset counts below the discontinuation threshold, discontinue study drug |
| CD4 (T helper cells), CD8 (cytotoxic T cells), or CD19 (B cells) absolute counts between LLN and discontinuation threshold or >33% reduction from baseline in CD4 (T helper cells), CD8 (cytotoxic T cells), or CD19 (B cells) absolute counts | Lymphocyte subset counts to be performed weekly until counts return to \geq LLN or no more than 33% reduction from baseline | Decision will be based upon lymphocyte subset counts and clinical judgment |

LLN = lower limit of normal.

- c. Subjects with clinical evidence of infection will have their CD4 (T helper cells), CD8 (cytotoxic T cells), and CD19 (B cells) absolute counts measured. Blood and other biological samples will also be collected for investigations of infective pathogens (eg,

serological tests, quantitative polymerase chain reaction, microscopy, and culture) where appropriate. In subjects with infection, if any of their absolute cell counts meets the discontinuation thresholds, study drug will be discontinued. All subjects with severe infections will be discontinued from study drug. All subjects with herpes zoster (shingles) or ocular herpes infections will be discontinued from study drug, regardless of severity of presentation. Subjects with mild or moderate infection may continue treatment with study drug unless otherwise clinically indicated or otherwise specified below. Specifically, when any of the CD4 (T helper cells), CD8 (cytotoxic T cells), and CD19 (B cells) absolute counts are between the LLN and the discontinuation thresholds or have shown >33% reduction from baseline, subjects with infections of moderate intensity will be discontinued from study drug (eg, subjects whose infections are not localized, or subjects who are systemically unwell, or who require systemic anti-infective drug treatment). All subjects with infection who are discontinued from study drug will be followed for a period of 12 weeks or until the infection resolves/ stabilizes or until the CD4 (T helper cells), CD8 (cytotoxic T cells), and CD19 (B cells) absolute counts have returned to >LLN (whichever comes latest).

Table 2 Study Drug Actions for Lymphocyte Subset Absolute Counts and Infection

| Criterion | Severity of Infection | | |
|--|--|---|------------------------|
| | Mild | Moderate | Severe |
| CD4 (T helper cells), CD8 (cytotoxic T cells), or CD19 (B cells) absolute counts below discontinuation threshold | Discontinue study drug | Discontinue study drug | Discontinue study drug |
| CD4 (T helper cells), CD8 (cytotoxic T cells), or CD19 (B cells) absolute counts between LLN and discontinuation threshold or >33% reduction from baseline in CD4 (T helper cells), CD8 (cytotoxic T cells), or CD19 (B cells) absolute counts | May continue treatment with study drug unless clinically indicated | Discontinue study drug | Discontinue study drug |
| CD4 (T helper cells), CD8 (cytotoxic T cells), or CD19 (B cells) absolute counts always >LLN and no reduction from baseline >33% | May continue treatment with study drug unless clinically indicated | May continue treatment with study drug unless clinically indicated (See (e) for exception) | Discontinue study drug |

LLN = lower limit of normal.

- d. A subject with any skin rash of moderate to severe intensity, or any rash lasting more than 72 hours regardless of severity (see (e) for exception), will be discontinued from study drug and a dermatological consult will be requested regardless of whether the rash is considered drug-related or due to other causes. For cases where the investigator suspects a drug rash, regardless of severity, the subject will be discontinued from study drug, a dermatological consult will be requested, and a skin biopsy will be performed to confirm the diagnosis. The skin rash will be treated as per standard care and will be followed up until resolution regardless of etiology or severity.
- e. Subjects who develop moderate to severe oral or genital herpes should be discontinued from study drug. Subjects who develop a mild case of oral or genital herpes may remain on study drug even if the event lasts more than 72 hours.

- f. Development of any of the following features on MRI: vasogenic edema, macrohemorrhage, an area of superficial siderosis, or a symptomatic microhemorrhage. If discontinued from study drug, subjects will undergo an ED Visit within 7 days after discontinuation and will attend the Follow-Up Visits 4 and 12 weeks after the last dose of study drug. They will also undertake an Unscheduled Visit (with MRI) at approximately 4 weeks after the visit at which such MRI features were first identified. An MRI will also be performed at approximately the time of the second Follow-Up Visit (Visit 20). Additional visits for safety may be arranged if clinically indicated in the opinion of the investigator, including after 12 weeks after the last dose of study drug. At any time during the treatment period, subjects who have asymptomatic, treatment-emergent microhemorrhages as detected by MRI, but none of the features which merit discontinuation of treatment (ie, vasogenic edema, macrohemorrhage, an area of superficial siderosis, or a symptomatic treatment-emergent microhemorrhage) may continue with treatment. These subjects will have safety assessments (including MRI) at approximately 4 weeks after the visit at which such MRI features were found. They will also continue with the scheduled MRI scans. Additional unscheduled MRI scans may be arranged on an individual subject basis in discussion with the study medical monitor.
- g. A postdose ECG with an average QTcF interval >500 msec from triplicate ECGs
- h. A postdose ECG with a QTcF interval increase from baseline >60 msec and a QTcF interval >450 msec as demonstrated from triplicate ECGs
- i. Any seizure (motor or non-motor)
- j. Pregnancy

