9.7.1.8.3 LABORATORY VALUES

Laboratory results will be summarized using International System of Units, as appropriate. For all quantitative parameters listed in [Section 9.5.1.5.3](#), the actual value and the change from baseline to each postbaseline visit and to the end of treatment (defined as the last on-treatment value) will be summarized by visit and treatment group using descriptive statistics. Qualitative parameters listed in [Section 9.5.1.5.3](#) will be summarized using frequencies (number and percentage of subjects), and changes from baseline to each postbaseline visit and to end of treatment will be reported using shift tables. Percentages will be based on the number of subjects with both nonmissing baseline and relevant postbaseline results.

Laboratory test results will be assigned a low/normal/high (LNH) classification according to whether the value was below (L), within (N), or above (H) the laboratory parameter's reference range. Within-treatment comparisons for each laboratory parameter will be based on 3-by-3 tables (shift tables) that compare the baseline LNH classification to the LNH classification at each postbaseline visit and at the end of treatment. Similar shift tables will also compare the baseline LNH classification to the LNH classification for the highest and lowest value during the treatment period.

[Appendix 1](#) (Sponsor's Grading for Laboratory Values) presents the criteria that will be used to identify subjects with treatment-emergent markedly abnormal laboratory values (TEMAVs). Except for phosphate, a TEMAV is defined as a postbaseline value with an increase from baseline to a Grade of 2 or higher. For phosphate, a TEMAV was defined as a postbaseline value with an increase from baseline to a Grade of 3 or higher. When displaying the incidence of TEMAVs, each subject may be counted once in the laboratory parameter high and in the laboratory parameter low categories, as applicable.

Lymphocyte subsets (ie, CD4 [T helper cells], CD8 [cytotoxic T cells], CD19 [B cells], CD16/CD56 [natural killer cells] and CD14 [macrophages]) and regulatory T cells will be summarized in the same manner as other laboratory parameters. Mean lymphocyte subsets and the mean change from baseline in lymphocyte subsets will also be displayed graphically over time by dose.

Serum IgG, IgM, and IgA will be measured and summarized in the same manner as other laboratory parameters.

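### Lymphocyte testing becomes weekly once counts fall, so the lowest-value shift table compares arms at unequal testing intensity; a scheduled-visit table should stand beside it

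*Protocol*

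**What the plan says.** Section 9.3.3(b) sets two triggers for weekly subset counts. Subjects with "absolute counts between the LLN and the discontinuation threshold will have lymphocyte subset counts performed on a weekly basis"; and subjects more than 33% below baseline in any of the three subsets "absolute counts will also have lymphocyte subset counts performed on a weekly basis". Table 1 in the same section gives the duration: "Lymphocyte subset counts to be performed weekly until counts return to" the LLN or above, or the fall is no more than 33%. Item (c) adds counts at infection: "Subjects with clinical evidence of infection will have their CD4", CD8 and CD19 counts measured. Section 9.5.1.5.3 describes the surface markers as one panel, so a trigger in one subset brings new values of the others.

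On analysis, Section 9.7.1.8.3 plans by-visit and end-of-treatment shift tables in low/normal/high (LNH) classes, and then: "Similar shift tables will also compare the baseline LNH classification to the LNH classification for the highest and lowest value during the treatment period". Lymphocyte subsets "will be summarized in the same manner as other laboratory parameters". Nothing in the section confines the lowest value to scheduled samples.

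**The concern.** A minimum tends to fall as more values enter it. Here the number of values depends on the outcome: a subject who drops by a third but is still within the normal range moves to weekly testing and gains extra chances of being classed low. Late in treatment the scheduled counts are 13 weeks apart (weeks 26, 39, 52, 65 and 78), so the contrast with weekly testing is large.

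The protocol expects a drug effect. Section 9.4.4 reports CD4 changes in Study 002 of -3.1% at 100 mg and +8.7% on placebo, and Section 7.1 mentions some CD4 reduction at 50 to 100 mg. If that effect is present, active arms trigger more weekly testing than placebo, and the arms' lowest values are minima over different numbers of tests. Immunological parameters are named in the second primary objective (Section 8.1), so the tables showing them should be comparable across doses.

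**Working it through.** **Schedule.** Visits 4 to 18 give 15 on-treatment subset counts. Adding Visit 19 gives 16, and Screening and Baseline make 18; 18 x 4 mL = 72 mL. This reproduces the Table 8 entry (18 collections, 72 mL). The protocol gives no figure for shift-table rates, so the size has to be simulated.

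**Drug effect.** From Section 9.4.4, relative to placebo: 0.969 / 1.087 = 0.891, or 11% lower (simple difference 3.1 + 8.7 = 11.8, about 12 points). At 200 mg, which is not used in this trial: (1 - 0.229) / 1.087 = 0.709, or 29% lower.

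**Assumptions not in the protocol.** Log-normal counts for three subsets, all shifted by the drug; LLN at about the 2.5th percentile; entry counts at or above LLN. Model 1: between-subject log SD 0.30, within-subject CV 15-25%. Model 2: between-subject log SD 0.35, within-subject log SD 0.10-0.25, with discontinuation at the confirmed threshold included. The infection trigger in item (c) was not simulated.

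**Result.** Active minus placebo, in percentage points, for subjects whose lowest CD4 is below LLN, with weekly counts running until both triggers clear:

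| Model | Drug effect | Within-subject variation | Scheduled only | All values | Excess |
|---|---|---|---|---|---|
| 2 | 11% | SD 0.10 | 5.4 | 5.7 | 0.3 |
| 2 | 11% | SD 0.15 | 6.2 | 7.1 | 0.9 |
| 2 | 11% | SD 0.25 | 7.3 | 10.3 | 3.0 |
| 1 | 12% | CV 20% | 10.4 | 13.1 | 2.7 |

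The Model 1 row comes from 10.9% placebo and 21.3% active (scheduled only) against 12.0% and 25.1% (all values), with a mean of 19 and 26 tests per subject. At a 12% effect and CV 25% the excess in Model 1 is about 4 points. With no drug effect the excess is 0, because both arms rise equally. At a 29% effect it is about 4 to 11 points, but that effect belongs to a dose not used here.

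**Which trigger does it** (Model 2, within-subject SD 0.15 and 0.25, 11% effect):

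| Testing driven by | Excess, points |
|---|---|
| CD4 below LLN only | 0.0 |
| CD4 more than 33% down only | 0.2 to 0.9 |
| All subsets, both triggers | 1.0 to 2.9 |

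A subject sent to weekly testing by a below-LLN CD4 is already classed low for CD4, so that route adds almost nothing. The excess comes from the 33% trigger and from retesting the whole panel when another subset triggers.

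**Robustness** (Model 2, 11% effect). With autocorrelated counts (rho 0.8) the excess is 1.1 to 2.9 points. If weekly counts stop as soon as either Table 1 condition is met, which is the literal wording, it is 0.7 to 1.4 points.

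**Ratios.** Model 1, 12% effect, CV 20%: scheduled only 21.3 / 10.9 = 1.95; all values 25.1 / 12.0 = 2.09. If both arms were tested weekly for 78 weeks, the ratio would be about 1.69 and the difference about 14.8 points.

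Model 2, 11% effect, SD 0.25: scheduled only 19.5 / 12.2 = 1.60; all values 24.6 / 14.3 = 1.72. Under the literal stopping rule, placebo is 12.2 + 1.3 = 13.5 and active 19.5 + 2.7 = 22.2, a ratio of 1.64.

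**The case against.** The strongest objection concerns the word overstated. The chance of ever being below LLN has no true value apart from a testing frequency. With both arms tested weekly, the difference in the Model 1 example is 14.8 points, above the planned table (13.1) and the scheduled-only table (10.4). At effects of 12% or less the planned difference is usually below the equal-weekly one; the reverse can occur with larger effects, higher variability or autocorrelation (29.4 against 28.1 points in one setting with a 20% effect). A reader might infer that the dose-placebo difference is simply exaggerated. That holds only against the fixed schedule. What remains is that the two arms are not measured on the same footing.

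Secondly, this is one descriptive table. The same section plans by-visit values, by-visit and end-of-treatment shift tables, and mean plots by dose, all essentially unaffected, and it describes the shift tables as within-treatment comparisons. A reader might infer that the Phase 3 dose choice would be distorted. Section 7 says only that the study's results will guide that choice; it does not tie it to this table.

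Thirdly, the size depends on assumed variability and on an effect seen at 100 mg, whose exposure Section 9.4.4 puts above that of the top dose here. The documents give that effect for CD4 only; shifting CD4 alone reduces the Model 1 excess from 2.7 to 1.2 points (11.7 against 10.5). This stands, and it limits the weight of the point.

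Fourthly, handling of unscheduled laboratory values is often left to the statistical analysis plan, which may already narrow the table. However, the protocol itself specifies the lowest value over the whole treatment period and applies it to subsets whose testing it makes outcome-dependent. Clarifying that sentence is reasonable.

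Finally, a worst-value safety table is expected to show every low count seen. That is right, and it argues against replacing the all-values table.

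**Conclusion.** The point holds in a limited form. If E2609 lowers counts, comparing arms on the all-values lowest-value table mixes drug effect with testing intensity. Against a scheduled-only table, the absolute difference in lowest CD4 below LLN is larger by roughly 0.3 to 4 points at an 11-12% effect, and by less under Table 1's literal stopping wording. The active/placebo ratio is slightly higher than under the fixed schedule (2.09 against 1.95 in the example), barely so under the literal stopping wording, and clearly higher than under equal weekly testing (1.69). The direction follows from the text; the size rests on assumed between- and within-subject variation, an assumed LLN and an effect borrowed from another dose and formulation.

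The rule amplifies a real difference and does not create one, so the documents do not support reading it as a source of false safety signals. This is a cheap improvement to one descriptive display and does not undermine the safety analysis.

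**What to change.** In Section 9.7.1.8.3:

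- Keep the highest/lowest-value shift table from all values, so that no low count is hidden.
- Add beside it the same table for lymphocyte subsets from scheduled-visit samples only.
- State that between-arm and by-dose comparisons are read from the scheduled-only table.
- Report the number of subset counts per subject by arm.

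The cost is a sentence or two, one extra table and one summary line. The scheduled-only table will omit lows seen only at triggered tests, which is why the all-values table stays. The monitoring rules in Section 9.3.3 are not touched.

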| Centralized dermatological assessment via photography ^g | | | | | | | | | X | | | X | X | X | X | X | X | X | | X | X |
| Neurological examination ^h | | | | | | | | | | | | X | | X | | X | X | X | X | X | X |
| Ophthalmic examination ⁱ | | | | | | | | | | | | | | | | | | | | | X |
| Concomitant medications ^j | | X | X | X | X | X | X | X | X | X | X | X | X | X | X | X | X | X | X | X | X |
| 12-lead ECG ^k | | | X | | X | | X | | X | | | X | | X | | X | X | X | X | X ^e | X |
| Clinical biochemistry and urinalysis | | | X | | X | | X | | X | | | X | X | X | X | X | X | X | X | X ^e | X |
| Complete blood count | | X | X | X | X | X | X | X | X | X | X | X | X | X | X | X | X | X | X | X ^e | X |
| Blood samples for lymphocyte subset analyses ^l | | X | X | X | X | X | X | X | X | X | X | X | X | X | X | X | X | X | X | X ^e | X |
| Blood samples for Igs ^m | | | | | X | | X | | X | | | X | | X | | X | X | X | X | X ^e | X |
| Blood samples for isolation of PBMCs | | | X | | | | | | X | | | | | | | | | | | | X |
| Urine pregnancy test (females of CBP only) | X ⁿ | | | | | | | | X | | | X | X | X | X | X | X | X | X | | X |
| Blood sample for storage for immune status ^o | | | | | X | | | | X | | | X | | X | | X | X | X | X | X | X |
| CBB and ISLT ^p | | | | | | | | | X | | | X | X | X | X | X | X | X | X | X | |
| MMSE ^p | | | | | | | | | X | | | X | X | X | X | X | X | X | X | X | |
| CDR ^p | | | | | | | | | X | | | X | X | X | X | X | X | X | X | X | |
| ADAS-cog ₁₄ ^p | | | | | | | | | X | | | X | X | X | X | X | X | X | X | X | |

| Table 7 Schedule of Procedures/Assessments in Study 202: Randomization Phase (Visit 3 through Visit 20) | | | | | | | | | | | | | | | | | | | | |
|---|---------------|---|----|----|----|----|----|----|----|-----|-----|-----|-----|-----|-----|-----|-----------------|-----------------|---------------------------|-----------------|
| Phase | Randomization | | | | | | | | | | | | | | | | | | UNS Visit ^d | |
| Period | Treatment | | | | | | | | | | | | | | | | Follow-Up | | | |
| Visit ^a | 3 | 4 | 5 | 6 | 7 | 8 | 9 | 10 | 11 | 12 | 13 | 14 | 15 | 16 | 17 | 18 | ED ^b | 19 ^c | | 20 ^c |
| Day | 1 | 8 | 15 | 22 | 29 | 43 | 57 | 71 | 85 | 113 | 141 | 183 | 274 | 365 | 456 | 547 | | 575 | | 631 |
| Week | 1 | 2 | 3 | 4 | 5 | 7 | 9 | 11 | 13 | 17 | 21 | 27 | 40 | 53 | 66 | 79 | | 83 | | 91 |
| Weeks elapsed since first dose | 0 | 1 | 2 | 3 | 4 | 6 | 8 | 10 | 12 | 16 | 20 | 26 | 39 | 52 | 65 | 78 | | 82 | | 90 |

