9.5.2.2 Description of Procedures/Assessments Schedule

Please refer to [Table 6](#) and [Table 7](#) for the timings of the procedures and assessments to be performed during the study. Screening assessments will be organized into 4 tiers (see [Table 6](#), [Section 9.1.1.1](#), and [Figure 2](#)).

See [Section 9.5.1](#) for a full description of the procedures and assessments to be performed during this study.

Table 8 presents the number of blood and CSF samples, and the total volume of blood and CSF that will be collected throughout the study. Additional samples may be taken at the discretion of the investigator if the results of any tests fall outside reference ranges or if clinical symptoms necessitate testing to ensure subject safety.

Table 8 Summary of Blood and CSF Sample Volumes

| Assessment | Total number of collection time points | Number of time points x volume per collection (mL whole blood or CSF) | | Total volume (mL whole blood or CSF) |
|--|--|---|---------------------------------|--------------------------------------|
| | | Screening and Baseline Periods | Treatment and Follow-Up Periods | |
| Blood | | | | |
| Chemistry | 12 | 2 x 2 mL | 10 x 2 mL | 24 mL |
| Hematology | 18 | 2 x 5 mL | 16 x 5 mL | 90 mL |
| Lymphocyte subset analyses | 18 | 2 x 4 mL | 16 x 4 mL | 72 mL |
| PBMC | 4 | 1 x 16 mL | 3 x 16 mL | 64 mL |
| IgA, IgM, IgG | 9 | 2 x 2 mL | 7 x 2 mL | 18 mL |
| PT, PTT for INR | 2 | 2 x 3 mL | None | 6 mL |
| Thyroid function tests (thyroid stimulating hormone, free triiodothyronine and free thyroxine) | 1 | 1 x 3 mL | None | 3 mL |
| Viral screen (Hepatitis B and C) | 1 | 1 x 4 mL | None | 4 mL |
| Viral characterization | 1 | 1 x 4 mL | None | 4 mL |
| Vitamin B12 | 1 | 1 x 2 mL | None | 2 mL |
| Serum pregnancy test | 1 | 1 x 2 mL | None | 2 mL |
| Tuberculosis (interferon-gamma release assays) | 1 | 1 x 3 mL | None | 3 mL |
| Sample for immune status | 8 | 1 x 4 mL | 7 x 4 mL | 32 mL |
| PD sample | 9 | 1 x 4 mL | 8 x 4 mL | 36 mL |
| PK analysis | 7 | 1 x 3 mL | 6 x 6 mL | 39 mL |
| Pharmacogenetic sample | 1 | 1 x 3 mL | None | 3 mL |
| All blood samples, total volume whole blood collected | | 80 mL | 322 mL | 402 mL |
| CSF | | | | |
| PD and PK samples | 3 | 1 x 12 mL | 2 x 12 mL | 36 mL |

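### Table 1 starts weekly lymphocyte counts on either of two triggers but lets them stop when either one is clear, so read literally the extra counts can end while a trigger persists

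*Protocol*

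**What the plan says.** Section 9.3.3 sets the lymphocyte safety rules in items (a) to (c) and Tables 1 and 2.

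- **Entry, Table 1 row 2.** The row applies to subjects with "absolute counts between LLN and discontinuation threshold or >33% reduction from baseline in CD4" cells, CD8 or CD19.
- **Action, same row.** The cell opens "Lymphocyte subset counts to be performed weekly until counts return to" and, after a greater-than-or-equal sign, closes "LLN or no more than 33% reduction from baseline".
- **Item (b).** One sentence requires weekly counts for subjects between the LLN and the discontinuation threshold. The next says that subjects more than 33% down in their "absolute counts will also have lymphocyte subset counts performed on a weekly basis". Neither sentence says when the weekly counts end.
- **Item (c).** For infected subjects taken off study drug, follow-up has three end conditions joined by 'or', with an explicit tie-break: 12 weeks, resolution or stabilisation of the infection, or until "absolute counts have returned to >LLN (whichever comes latest").
- **Table 2, bottom row.** The state with neither problem is described as "absolute counts always >LLN and no reduction from baseline >33"%.

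The other version of Section 9.3.3 in the protocol file, whose Table 1 is headed Study Conduct Actions, has the same 'or' in the stop condition.

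**The concern.** The two triggers are alternatives: either one puts a subject on weekly counts. The counts should therefore end only when neither is present. The printed cell ends them when either clearing condition is true, and it is the only stop rule given for these counts. It also sits badly with item (b), which treats each trigger as sufficient by itself.

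Weekly counts are how a subject with a known low or falling subset is followed between scheduled visits. Section 7.1 names lymphocytes and their subsets as suitable markers for immunotoxicity. It also reports some evidence of CD4 reduction by Day 15 at 50 to 100 mg. The top dose here is 50 mg, and dosing goes from 14 days to 18 months. Two sites could read the cell differently and stop the extra counts at different points, one of them while the subject is still below the LLN or still more than 33% down.

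**Working it through.** There is no plan figure to reproduce. The check is one of logic, visit spacing and illustration.

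**1. Entry against exit.** Let A be a count between the LLN and the discontinuation threshold, and B a fall of more than 33% from baseline. Entry is A or B. The printed exit is not-A or not-B. The complement of entry is not-A and not-B.

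| A | B | Weekly counts triggered | Printed exit met | Exit met with 'and' |
|---|---|---|---|---|
| no | no | no | yes | yes |
| no | yes | yes | **yes** | no |
| yes | no | yes | **yes** | no |
| yes | yes | yes | no | no |

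In 2 of the 3 triggered states the printed exit is already met. In the third it becomes met as soon as either trigger clears. With 'and', the exit is never met while a trigger is present.

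**2. What lies between scheduled counts.** Table 7 schedules "Blood samples for lymphocyte subset analyses" at every visit from Day 8 to Day 547. Weekly counts falling between two scheduled ones = gap/7 − 1.

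| Days | Gap (days) | Weekly counts in between |
|---|---|---|
| 8 to 29 | 7 | 7/7 − 1 = 0 |
| 29 to 85 | 14 | 14/7 − 1 = 1 |
| 85 to 113, 113 to 141 | 28 | 28/7 − 1 = 3 |
| 141 to 183 | 42 | 42/7 − 1 = 5 |
| 183 to 274, 365, 456, 547 | 91 | 91/7 − 1 = 12 |

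These are maxima per interval. They assume that weekly counts stop at a scheduled visit and that the trigger lasts to the next one.

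**3. Two-trigger illustration.** The protocol gives no LLN for CD4. I assume 450 cells/µL, with a range of 400 to 500. Trigger B clears at 0.67 × baseline.

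- *Baseline 900, nadir 420, recovery to 460.* At nadir 1 − 420/900 = 53%, and the count is below 450, so both triggers hold. At 460 the count is above the LLN, but 1 − 460/900 = 49%. The printed rule stops; 'and' continues to 0.67 × 900 = 603.
- *Baseline 600, nadir 390, recovery to 410.* At nadir 1 − 390/600 = 35%, and the count is below 450. At 410, 1 − 410/600 = 32%, but the count is still below the LLN. The printed rule stops; 'and' continues to 450.

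These exact counts do not work at every assumed LLN. The first needs an LLN above 420 and no higher than 460; the second needs one above 410. The pattern itself is general. The LLN is regained first when baseline exceeds LLN/0.67 (400/0.67 = 597; 450/0.67 = 672; 500/0.67 = 746). Below that, the 33% condition clears first. For a baseline of 900, any recovery value from the LLN up to 603 stops under 'or' while trigger B persists, at any LLN from 400 to 500.

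**The case against.** The strongest reply is that item (b) settles the matter. It imposes weekly counts as two separate duties, each tied to the subject's current state, so a subject still below the LLN or still more than 33% down remains under one of them. Row 2 of Table 1 can also be read as keyed to current status. The literal reading would make the row empty for every single-trigger subject, which cannot be meant. The verb 'return' suggests that each trigger ends on its own clearance, and on that reading an uncleared second trigger keeps running.

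There are other safeguards. Section 9.5.2.2 allows extra samples at the investigator's discretion when a result is out of range. Table 7 allows unscheduled visits with subset counts (note d) and repeats out-of-range subsets at Visit 20 (note e). Table 2 serves a different purpose, and item (c) covers infected subjects already off drug.

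Much of this stands. It shows what was probably intended and limits the consequence. It does not make the printed cell correct. Nothing in the cell says that the conditions apply respectively, and a site that follows the only written stop rule may stop early. The extra samples are discretionary, whereas the weekly counts are mandatory.

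**Conclusion.** The cell is wrong as written: its exit is not the complement of its entry, and it conflicts with item (b). The finding rests on a literal reading and covers only the additional weekly counts. Scheduled counts, the confirmed below-threshold stop, testing at infection and Table 2 are unchanged.

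The exposure is largest after Month 6, when up to 12 weekly counts per 91-day interval could lapse in a subject who still meets a trigger. The conclusion does not depend on the assumed CD4 LLN, which enters only the illustration. How many subjects would be affected cannot be derived from the protocol, and no endpoint, error rate or sample size is touched. It should be corrected because the cell governs a central safeguard and the correction is very cheap.

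**What to change.** In Table 1 row 2, replace 'or' with 'and' in the stop condition, so that weekly counts continue until counts are back to at least the LLN **and** no more than 33% below baseline. To remove any doubt across subsets, it could say that CD4, CD8 and CD19 must all meet both conditions. No threshold changes.

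The cost is one word at the next amendment and a memo to sites. Some subjects will stay on weekly draws longer. At the 4 mL per draw in Table 8 ("Lymphocyte subset analyses | 18 | 2 x 4 mL | 16 x 4 mL | 72 mL"), that is at most 12 × 4 = 48 mL per 13-week interval after Month 6, for draws that item (b) already calls for.
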